6.2.1. Preparation and Dispensing

The amount of IP shipped to the site will be based on the participant's body weight measured at the Baseline Visit (Visit 2) for Year 1 IP administration and at Day 328 Visit (Visit 18) for Year 2 IP administration, and on the and IP concentration per vial. Approximately 14 to 45 days, depending on the site location, is required for shipment of IP.

For participants who undergo Day 328 (Visit 18) during a study dosing pause, the amount of IP to be shipped to the site will be determined once the study has been restarted. Therefore, the weight collected at Day 328 (Visit 18) will not be entered into the interactive response technology drug management system during the study dosing pause. Participants will be evaluated for Year 2 IP eligibility when the study is restarted.

The IP will be dispensed using an interactive response technology (IRT) drug management system for the dosing visits. A qualified staff member will dispense the IP via unique container numbers on the vials provided, in quantities appropriate for individual participant dosing once the participant is confirmed to be eligible for IP administration and admitted to the site for dosing.

Preparation of IP should be performed by appropriately qualified, Good Clinical Practice (GCP)-trained, and preferably gene therapy-experienced pharmacist as allowed by local, state, and institutional guidance. It is strongly recommended to prepare the IP dosing solution as close to the administration time on the dosing day as possible. See the IP manual for instructions on how to prepare the IP for administration. The IP manual will need to be reviewed and acknowledged by any site staff preparing and/or administering the product.

IP will be prepared by qualified blinded site personnel according to the IP manual. The IP will be administered to participants in a blinded fashion.

Only qualified personnel who are familiar with procedures that minimize undue exposure to themselves and to the environment should undertake the preparation, handling, and safe disposal of gene therapy agents. Please refer to the IP manual for detailed handling instructions.

6.3. Measures to Minimize Bias: Randomization and Blinding

6.3.1. Allocation to Investigational Product

Eligible participants will be randomized into Cohort 1 or Cohort 2 (See [Section 4.1](#)) in a 2:1 fashion, using the method of permuted blocks within each randomization strata, where the strata are defined by their age at Screening (<6 or \geq 6 years old) with no more than approximately 55% of dosed participants in either of the Screening age strata. Enrollment will be assessed periodically, and if an imbalance is noted, enrollment of the overrepresented stratum may be paused until a more balanced distribution is achieved. The randomization schedule is generated by the Sponsor. Personnel who are directly involved in the study conduct are blinded to the randomization schedule.

Allocation of eligible participants to study intervention (see [Section 4.1](#) for additional details) will proceed through the use of an IRT system. The site personnel (study coordinator or specified designee) will be required to enter or select information including, but not limited to, the user's identification (ID) and password, the protocol number, and the participant number. The IRT system will provide a confirmation report containing the participant number, randomization number, and container numbers assigned. The confirmation report must be stored in the site's files.

The eligible sibling(s) will receive the same treatment with approximately the same timing (as long as the siblings were strictly separated from each other until both have received IP) and sequence based on the Cohort to which the participant is randomized (see [Section 5.3](#)) and study intervention for the sibling(s) will be manually assigned in the system by the IRT support team. Siblings will receive their own unique participant number.

IP will be dispensed at the study visits summarized in the [SoA](#).

The study specific IRT reference manual will provide the contact information and further details on the use of the IRT system.

6.3.2. Breaking the Blind

The participants, Sponsor, vendors, and study personnel will be blinded to treatment allocation, except for an unblinded, medically-qualified monitor (medical monitor), independent from the team conducting and monitoring the study as defined in [Section 7.1](#).

The IRT will be programmed with blind breaking instructions. In case of an emergency, the Investigator has the sole responsibility for determining if unblinding of a participant's treatment assignment is warranted. Participant safety must always be the first consideration in making such a determination. If the Investigator decides that unblinding is warranted, the Investigator should make every effort to contact the Sponsor prior to unblinding a participant's treatment assignment unless this could delay further management of the participant. If a participant's treatment assignment is unblinded, the Sponsor must be notified by the Investigator within 24 hours after breaking the blind. The date and reason that the blind was broken must be recorded in the source documentation and case report form

(CRF)/data collection tool (DCT). Unblinding will not necessarily lead to study discontinuation.

The study specific IRT reference manual will provide the contact information and further details on the use of the IRT system to break the blind.

6.3.3. Sensitive Clinical Data

Select safety and immunogenicity results

In order to prevent the functional unblinding of the treatment assignment, the results of the following assessments will not be shared with the study team or the site after Year 1 IP administration and throughout the blinded portion of the study:

- CK;
- AST and ALT;
- NAb to AAV9 (See [Section 7.1](#));
- ELISpot to AAV9 and mini-dystrophin;
- ADA to AAV9 and mini-dystrophin;
- C3 and C4.

An unblinded medically qualified monitor (medical monitor) will review the results of CK, AST and ALT, NAb to AAV9, and ADA to mini-dystrophin for each participant on an ongoing basis and will decide if any result(s) should be repeated and/or shared with the site and the study team, due to a judgement that the results could reflect a safety issue (eg, liver injury, myositis, other immunological reaction).

If a participant in Cohort 2 presents with a positive test for NAb to AAV9 on the sample taken at the Day 34 (Visit 13) he will be withdrawn from the study given that it would already be determined at that time that he is not be eligible for fordadistrogene movaparvovec administration at Year 2. If this situation occurs while the study is still accruing participants, an additional 2 participants may be randomized for each Cohort 2 participant who is withdrawn.

Additionally, if the threshold of laboratory abnormalities for a potential drug-induced liver injury (DILI) case has been met (see [Appendix 6](#)), the results for ALT and AST will be shared with the site and the study team until the potential DILI has been investigated and it is considered resolved.

If a clinical event occurs that, in the opinion of the Sponsor and/or the Investigator, could be due to an immunological reaction, additional ad-hoc assessments of NAb to AAV9, ADA to AAV9 and mini-dystrophin, ELISpot to AAV9 and mini-dystrophin may be conducted if

considered indicated by the Sponsor and/or the Investigator for the interpretation and/or the management of the immunological reaction. The results of these tests will be shared with the site and the study team.

Additionally, to further prevent the introduction of bias in the scoring of the functional assessments, all possible measures should be put into place to prevent the clinical evaluators from viewing the participants' medical records/database where relevant information that could lead to functional unblinding, such as the occurrence of lab abnormalities or AEs/SAEs, may be recorded.

Viral vector shedding results

In order to prevent the functional unblinding of the treatment assignment, the results of the following assessments will not be shared with the site or the study team throughout the blinded portion of the study:

- Viral vector shedding.

An unblinded qualified Sponsor representative, independent and firewalled from the study team, will review the viral vector shedding results for each participant on an ongoing basis. The unblinded qualified Sponsor representative will communicate to the site when sampling in a given matrix (ie, blood, urine, or saliva) for each participant can be stopped. For Cohort 1 participants sampling for each matrix will be stopped when two consecutive samples test negative. To prevent unblinding, sampling will also be stopped for a matched Cohort 2 participant.

Muscle biopsy results

In order to prevent the functional unblinding of the treatment assignment, the results of the following assessments will not be shared with the site or the study team throughout the blinded portion of the study:

- Percent normal mini-dystrophin expression level, quantified by LC-MS.
- Percent of muscle fibers expressing mini-dystrophin, assessed by immunohistochemistry.

No review of these results will be conducted by the unblinded medical monitor.

Year 2 IP eligibility laboratory results

Given that the below eligibility assessment does not apply to Cohort 1 for Year 2 IP administration and in order to prevent unblinding of the treatment assignment, when assessing Cohort 2 participants' eligibility for Year 2 IP administration, the following test

results will not be shared with the sites and the study team, and will only be reviewed by an unblinded medical monitor (see [Section 7.1](#)).

- Laboratory results at Day 360 (Visit 19):

 NAb to AAV9;

 Absolute neutrophil count <1000 cells/mm³;

 Platelets <150 x 10³/µl;

 Cystatin C >1.2 x ULN;

 Positive hepatitis A virus (anti-HAV) immunoglobulin M, hepatitis B surface antigen (HbsAg), and/or hepatitis C antibody (HCVAb);

 Markers of hepatic inflammation or overt or occult cirrhosis as evidenced by one or more of the following:

- PT > ULN; prolonged INR >ULN;
- GLDH >2 x ULN;
- Total bilirubin >1.5 x ULN (unless the participant has a history of Gilbert disease) and direct bilirubin >0.5 mg/dL;
- GGT >1.5 x ULN.

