2.3.3.3. Immunity to AAV9

Following administration of fordadistrogene movaparvovec, immunity to AAV9 will be induced. As a result, it will not be possible for a participant treated with fordadistrogene movaparvovec to receive an additional dose of fordadistrogene movaparvovec or any other therapy that utilizes AAV9. Antibodies to AAV9 might also react to other serotypes of AAV and thus prevent treatment with therapies using these other vectors. At this time, there is no known means to mitigate this risk.

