4.2. Scientific Rationale for Study Design

4.2.1. Rationale for Inclusion of a Placebo Control Group

The purpose of this Phase 3 study is to evaluate the safety and efficacy of a single IV administration of fordadistrogene movaparvovec compared to placebo in participants with DMD. The results of this study will be used to support submission for registration of this therapy for treatment of DMD. There are several reasons that a placebo-controlled design is necessary to generate robust results. First, there is considerable variability in the disease progression and therefore improved function among treated participants can be attributed to fordadistrogene movaparvovec only when compared to participants randomized to placebo. Second, in the age range of the study population, some young participants may be improving their motor function as a result of ongoing development and the only way to differentiate this improvement from that which may occur as a result of fordadistrogene movaparvovec is by comparison to a placebo group. Third, there are not adequate data on the impact of small changes in glucocorticoid regimen, as are allowed in this study, to differentiate this effect from that of fordadistrogene movaparvovec. Ensuring that the study remains blinded through the primary analysis is important because knowledge of treatment assignment can bias performance and evaluation of functional assessments.

Those randomized to Cohort 2 will receive fordadistrogene movaparvovec after completing the first year of observation, provided they remain eligible. This will enable all eligible participants to receive treatment with fordadistrogene movaparvovec.

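### Ad-hoc NAb, ADA and ELISpot results go to the site and the blinded study team with no medical-monitor decision, recipient limit or unblinding record

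*Protocol*

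**What the plan says.** Section 6.3.3 (Sensitive Clinical Data) lists CK, AST/ALT, C3/C4, NAb to AAV9, and ELISpot and ADA to AAV9 and to mini-dystrophin. For these, to prevent functional unblinding, "the results of the following assessments will not be shared with the study team or the site after Year 1 IP administration" and for the rest of the blinded period.

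For CK, AST/ALT, NAb and ADA to mini-dystrophin, an unblinded medical monitor reviews results continuously and "will decide if any result(s) should be repeated and/or shared with the site and the study team", the test being whether they could reflect a safety issue.

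A separate paragraph covers clinical events that the Sponsor or the Investigator thinks may be immunological. In that case "additional ad-hoc assessments of NAb to AAV9, ADA to AAV9 and mini-dystrophin, ELISpot to AAV9 and mini-dystrophin may be conducted if" they are "considered indicated by the Sponsor and/or the Investigator for the interpretation and/or the management of the immunological reaction". Once the tests have been run, the rule is unconditional: "The results of these tests will be shared with the site and the study team".

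Three other places bear on this:
- Section 2.3.3.3: "Following administration of fordadistrogene movaparvovec, immunity to AAV9 will be induced".
- Section 6.3.2 blinds participants, Sponsor, vendors and study personnel, with the medical monitor as the exception. For an emergency code break it requires Sponsor notification within 24 hours, and "The date and reason that the blind was broken must be recorded in the source documentation" and in the CRF.
- Section 4.2.1 justifies blinding through the primary analysis because "knowledge of treatment assignment can bias performance and evaluation of functional assessments".

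**The concern.** One section treats the same assays in two opposite ways. Scheduled results are withheld because they can reveal treatment. Ad-hoc results are sent by default both to the site, where they may be needed for care, and to the study team, which is meant to stay blinded. The ad-hoc paragraph does not mention the medical monitor, the staff who need the result, or section 6.3.2.

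At stake is the integrity of the blind before Week 52. Section 2.3.2 places the risk of immune reaction to vector and transgene with the active product, so releases are likely to fall unevenly between cohorts. Without a record of who received a revealing result and when, the effect on the primary and secondary endpoints is harder to examine.

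**Working it through.** The plan states no figure for this point, so there is none to reproduce. The check compares passages and asks how informative a result is.

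**1. Status at dosing.** Exclusion criterion 6 removes NAb-positive boys at Screening. The Year 1 Schedule of Activities (section 1.3.1, NAb footnote) bars dosing without a negative sample taken 55 days or less beforehand. Both cohorts therefore start NAb-negative.

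**2. What a post-dose NAb result reveals.** Let s be the probability that a Cohort 1 boy tests positive at a given time, and c the same probability for a Cohort 2 boy. Randomization is 2:1 (section 4.1).
- After a positive result, odds of active to placebo = 2 × s/c.
- After a negative result, odds = 2 × (1 − s)/(1 − c).

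The protocol gives neither s nor c, but their direction is clear. Section 2.3.3.3 implies that s becomes high once immunity has developed. Sections 5.4, 5.5.3 and 8.8.6 recognise transmission by household contact, and section 6.3.3 foresees positive Cohort 2 boys at Day 34, so c is not zero. Because those boys are withdrawn, c falls among those still under blinded follow-up. A positive result therefore points strongly to the active product without proving it.

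Before seroconversion, s and c are both near 0 and the odds after a negative result stay near 2 × 1/1 = 2, which is the allocation ratio. An early negative tells the reader almost nothing. The protocol gives no time to seroconversion, so the point at which a negative becomes informative is unknown.

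**3. ADA and ELISpot.** No positivity rates are given. A response to mini-dystrophin would point towards the active product, but how strongly cannot be stated.

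**4. Comparison with the protocol's other release rules.**

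| Result | Trigger | Who decides or receives |
|---|---|---|
| Scheduled NAb, ADA to mini-dystrophin (6.3.3) | Possible safety issue | Medical monitor decides |
| ALT/AST in potential DILI (6.3.3, Appendix 6) | Laboratory threshold; ends on resolution | Site and study team |
| Ad-hoc muscle biopsy (8.1.3) | Muscle or cardiac SAE | Analysed blinded unless Investigator or Sponsor decides otherwise |
| Viral shedding (6.3.3, 8.8.5) | Continuous review | Firewalled Sponsor representative |
| Ad-hoc NAb, ADA, ELISpot (6.3.3) | Opinion that the event may be immunological and testing is indicated | Site and study team; no gate, no end point |

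The last row has the loosest trigger, and it covers assays that the section itself regards as unblinding.

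**5. Who is shielded.** Section 6.3.3 asks for all possible measures to keep clinical evaluators away from records that could unblind them. It does not extend this to three groups:
- Investigators.
- Caregivers, who complete the Modified PODCI scales (section 8.1.7.1.1), which are secondary endpoints.
- The study team.

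Section 4.2.1 is also concerned with the child's performance, which shielding the evaluator does not address. Section 6.5.1 allows temporary glucocorticoid increases after consultation with the Sponsor, and section 4.2.1 says the effect of small regimen changes is not well known. Knowledge of treatment could therefore enter decisions that bear on Week 52 function.

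**The case against.** The strongest reply is that this is a deliberate safety exception. A possible immune reaction to a gene therapy must be interpreted quickly, the Sponsor may itself judge that testing is indicated, and the preceding paragraph shares ALT/AST in potential DILI on similar lines. This stands as far as access for care is concerned, and results must remain available to those managing the event. It does not explain default release to the study team. Section 4.1 describes that team's ongoing safety review as blinded, and the DILI rule at least has a laboratory threshold and an end.

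Further limits also stand:
- A reader might infer that every suspected immune event breaks the blind. It does not: testing is optional and must be judged indicated, and an untested event releases nothing.
- A reader might treat post-dose NAb as the treatment code. Foreseen Cohort 2 positives and the missing seroconversion timing rule that out.
- A reader might assume the medical monitor already gates all the scheduled immunology results. The stated remit omits ELISpot and ADA to AAV9.
- The evaluator safeguard is real and lowers the risk to NSAA scoring.
- AEs and SAEs are recorded on the CRF (section 8.3.1.2) and the tests leave laboratory records, so affected boys could probably be reconstructed afterwards. What is missing is a prospective record of each release as a potential unblinding.
- Local laboratory results already visible to sites may hint at treatment, so the additional unblinding from these assays is unknown.

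**Conclusion.** The point holds in limited form. When ad-hoc NAb, ADA or ELISpot tests are actually run, section 6.3.3 sends potentially revealing results to the site and the blinded study team with no monitor decision, no recipient limit and no unblinding record. This conflicts with the purpose the section gives for withholding the same assays.

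The number of participants affected cannot be estimated from the protocol. It is tempting to apply the Phase 1b experience in section 2.2.6, where 2 of 6 high-dose boys had complement-mediated SAEs, but that is not a testing rate. Sections 6.5.1 and 8.2.10 recognise that picture from platelets, hemolysis markers, creatinine and urine, and nothing says these immunology assays would be drawn.

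Nor do the documents support a claim that NSAA scoring is directly compromised. The residual risk runs through investigators, caregivers and the study team. The PODCI scales are secondary endpoints outside the fixed testing sequence in section 9.1, which limits the confirmatory consequence of caregiver knowledge.

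The conclusion rests on two readings: that section 2.3.3.3 implies a high post-dose NAb positivity rate in Cohort 1 once immunity has developed, and that no other rule in the protocol restricts the release. The change is worth making because it costs little.

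**What to change.** Amend the last sentence of the ad-hoc paragraph in section 6.3.3 so that:
1. Ad-hoc NAb, ADA and ELISpot results go to the existing unblinded medical monitor, whose stated remit is extended to ELISpot and ADA to AAV9.
2. The results are made available without delay to those managing the event, as needed to interpret or manage it. What is needed, and when, remains the investigators' judgement.
3. The results are not sent by default to the blinded study team or to clinical evaluators.
4. Each release is recorded with its date and reason as a potential unblinding, in the manner of section 6.3.2, so that affected participants can be identified in a sensitivity analysis.

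The cost is one administrative step and a log entry per release, plus the wider remit for the monitor. Emergency unblinding and access for patient care are unchanged.

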6.4. Study Intervention Compliance

The IP will be administered by the appropriately designated study staff at the Investigator site.

6.5. Concomitant Therapy

6.5.1. Permitted Therapies

Background glucocorticoid regimen (daily dose of ≥ 0.5 mg/kg/day prednisone or prednisolone, or ≥ 0.75 mg/kg/day deflazacort). There should be no changes to the background glucocorticoid regimen in the first two years of the study, except as described for the protocol-mandated glucocorticoid regimen, below. A change to the glucocorticoid regimen is defined as:

- A change >0.2 mg/kg in daily dose;
- A change in the specific glucocorticoid (prednisone, prednisolone, or deflazacort);
- A change in regimen (ie, from daily to any non-daily).

This definition also applies during the 3 months before the Screening Visit (Visit 1).

After two years (Day 749), any change to the background glucocorticoid regimen will be permitted.

Protocol-mandated glucocorticoid regimen for Year 1 and Year 2: to mitigate the risk of an immune response, participants will temporarily replace their background glucocorticoid regimen as follows:

1. Between 1 and 4 hours prior to IP administration: single dose of IV methylprednisolone 2 mg/kg. **Note:** Participants must be instructed to not take their background glucocorticoid dose on Day 1 (Visit 3) and on Day 390 (Visit 20).
2. From 1 to 15 days post-IP administration: 2 mg/kg/day oral prednisone or prednisolone.
3. From 16 to 30 days post-IP administration: 1.5 mg/kg/day oral prednisone or prednisolone.
4. From 31 to 60 days post-IP administration: 1.0 mg/kg/day oral prednisone or prednisolone.
5. From 61 to 90 days post-IP administration: 0.75 mg/kg/day oral prednisone or prednisolone.

A temporary increase in the daily dose of glucocorticoids, protocol mandated or background regimen, will be allowed only if medically required, after consultation with the Sponsor.

Following IP administration, participants with vomiting who cannot tolerate oral medications can receive IV glucocorticoids instead of oral glucocorticoids, per the clinical judgement of the Investigator. The dose of IV glucocorticoids must be consistent with the requirements of the protocol. The participants must return to oral glucocorticoids as soon as the Investigator considers that it is safe to do so.

Participants may return to their background glucocorticoid regimen after 90 days post-IP administration as long as there is no immune response or other clinical indication.

Cohort 1 participants confirmed to meet exclusion criterion 15 and participants who declined Year 2 IP administration will not receive their protocol-mandated glucocorticoid regimen in Year 2 and will continue receiving their background glucocorticoid treatment during Year 2, see [Appendix 12](#) and [Section 7.2.1](#).

Participants with delayed Year 2 IP administration will not receive their protocol-mandated glucocorticoid regimen until the pause is lifted and Year 2 IP administration takes place; they will remain on their background glucocorticoid regimen until then, see [Section 5.3.2](#).

Eculizumab

Treatment with one or more doses of the complement inhibitor, eculizumab, should be considered by the Investigator, according to the local prescribing information, for any participant who presents with a clinical picture of complement-mediated thrombotic microangiopathy. Signs consistent with atypical hemolytic uremic syndrome (aHUS) that would indicate the need for treatment include:

1. Creatinine $>2 \times$ Screening value; OR
2. Platelets $<75 \times 10^3/\mu\text{l}$ AND either (a) or (b):
 - a. Evidence of hemolysis:
 - Haptoglobin $<\text{LLN}$ or reduced to $<50\%$ from Screening value (Year 1) or from Visit 19 value (Year 2); or
 - Schistocytes on blood smear.
 - b. Evidence of nephropathy:
 - Anuria >12 hours; or
 - $\geq 2+$ blood or protein on urine dipstick; or
 - An increase of $>50\%$ in serum creatinine from Screening value.

Because the use of eculizumab increases the risk of contracting serious meningococcal infections, participants who have no contraindications and who have not previously received a vaccination against meningococcus or whose last vaccination at the time of the Screening Visit (Visit 1) is outside the time period of active coverage specified by the vaccine manufacturer must receive at least one dose of meningococcal conjugate (MenACWY) vaccine as early as possible in the Screening Period and not later than 30 days before IP administration. If they receive eculizumab, and depending on the duration of the treatment with eculizumab, a decision will be made as to whether they should receive a second dose of meningococcal vaccination or antibiotic prophylaxis, at the discretion of the Investigator. Participants must also receive serogroup B meningococcal (MenB) vaccination if indicated by national vaccination guidelines. The Investigator must evaluate the immunization status against meningococcus and any other locally required immunization for all participants at Screening (Visit 1); local eculizumab prescribing information, including additional vaccination, and other requirements must also be followed as needed. Additionally, all sites must have the MenACWY vaccine, MenB vaccine (if recommended in the national vaccination guidelines) and eculizumab available for all participants (eculizumab should be available for the first 2 months after IP administration at Year 1 and at Year 2). For participants who cannot receive meningococcal vaccination, antibiotic coverage must be provided simultaneously with eculizumab.

Participants who experience an event compatible with aHUS may be screened for a genetic predisposition to aHUS, as determined by the Investigator in consultation with the Sponsor to increase the understanding of the risk of developing aHUS (see [Appendix 2](#)).

Antiemetics

At the discretion of the Investigator, participants may be administered an oral antiemetic such as oral ondansetron following IP administration and following the local prescribing information to prevent or treat symptoms of nausea and vomiting. Participants (and/or caregivers) should be instructed to contact the site if vomiting continues despite anti-emetic treatment. If required, an IV antiemetic such as ondansetron may be administered by the site.

Anesthesia

Participants will also receive anesthesia according to the site standard of care for the muscle biopsies obtained in this study.

Vaccines

Participants will be able to receive any required live attenuated vaccine(s) only during the following periods:

1. Up to 90 days before Day 1 (Visit 3).
2. Day 60 (Visit 14) to Day 300. In addition, participants in Cohort 1 confirmed to meet exclusion criterion 15 will be allowed to receive any required live attenuated vaccine(s) for the remainder of the study. For details on the retrospective assessment of exclusion criterion 15, please see [Appendix 12](#).
3. Day 450 until the end of the study.

Participants will be able to receive an inactivated vaccine (eg, influenza, meningococcal, pneumococcal, *Haemophilus influenzae*) only during the following periods:

1. Up to 30 days before Day 1 (Visit 3)
2. Day 60 to Day 360 (Visit 19). In addition, participants in Cohort 1 confirmed to meet exclusion criterion 15 will be allowed to receive any required inactivated vaccine(s) for the remainder of the study. For details on the retrospective assessment of exclusion criterion 15, please see [Appendix 12](#).
3. Day 450 until the end of the study.

Participants will be able to receive an mRNA, or DNA-based, or non-replicating viral vector vaccine (eg, against SARS-CoV2) only during the following periods:

1. Up to 30 days before Day 1 (Visit 3)

2. Day 60 to Day 360 (Visit 19). In addition, participants in Cohort 1 confirmed to meet exclusion criterion 15 will be allowed to receive any required mRNA, or DNA-based, or non-replicating viral vector vaccine(s) (eg, against SARS-CoV2) for the remainder of the study. For details on the retrospective assessment of exclusion criterion 15, please see [Appendix 12](#).
3. Day 450 until the end of the study.

Other medications

With the exception of any prohibited therapies, other medications may be used if deemed necessary by the Investigator.

